STUDY PROTOCOL

This document contains two linked Protocols for the NIHR HTA funded study 'In-home Tracking of glaucoma: Reliability, Acceptability, and Cost: the I-TRAC Study' [NIHR 129248]. The Protocols were developed separately on guidance from Sponsor as the first protocol describes a work package that does not require R&D approval (but do require Institutional REC approval) where as the second Protocol research activities do require NHS REC and R&D approval. These two Protocols detail the following:

- 1. In-home Tracking of glaucoma Work Package 1 [*pages 2-14*]. This Protocol details the first work package of the proposed project which aims to identify which glaucoma patients are most appropriate for home monitoring (e.g. all patients, or those with stable disease, or those with severe glaucoma?). This will be achieved through a survey of Consultant Ophthalmologists who routinely treat patients with glaucoma.
- 2. In-home Tracking of glaucoma Work Packages 2-4 [pages 15 48]. This second Protocol details the substantive component of the I-TRAC project which aims to determine the feasibility and acceptability of digital technologies to monitor glaucoma at home and inform the possible need and design of a definitive evaluative study. This will be achieved through a mixed methods multi-phase programme of activity using interviews, focus groups, questionnaires and assessment of digital technologies in practice.

Non-CTIMP Protocol Template

Study Protocol

Full Title:	In-home Tracking of glaucoma Work Package 1:
Study Acronym:	I-TRAC WP1
Sponsor:	University of Aberdeen
Sponsor Reference Number:	Not applicable
Funder:	National Institute for Health Research, Health Technology Assessment Programme
Chief Investigator:	[name]
REC Reference Number:	CERB/2020/5/1963
R&D Reference Number:	Not applicable
ISRCTN / Clinicaltrials.gov No:	Not applicable
Version Number and Date:	Version 2

I-TRAC WP1 V2 210920

Protocol Approval

Signatures

By signing this document I am confirming that I have read, understood and approve the protocol for the above study.

[name] Chief Investigator [name] Signature

21st September 2020 Date

Version	Date	Change
1	180820	Approval of V1
2	210920	Change to also include the UK & Eire Glaucoma Society (UKEGS) in
		survey.

List of Abbreviations

CI	Chief Investigator
CNORIS	Clinical Negligence and Other Risks Scheme
CRF	Case Report Form
DMC	Data Monitoring Committee
GCP	Good Clinical Practice
ISF	Investigator Site File
PI	Principal Investigator
PMG	Project Management Group
R&D	Research and Development
REC	Research Ethics Committee
SOP	Standard Operating Procedure
TMF/SMF	Trial/Study Master File
TSC	Trial/Study Steering Committee

Summary

Glaucoma is a common chronic eye condition and the second commonest cause of blindness in the UK. It is typically influenced by the pressure in the eye (intraocular pressure) being too high, for a particular person. Glaucoma impairs mainly the peripheral vision (visual field). Treatments reduce eye pressure to delay or stop glaucoma getting worse. However, in some glaucoma may still progress, so patients need regular monitoring at hospital eye services where they have their eye pressure and the visual field measured. This allows doctors to assess effectiveness of current treatment and detect glaucoma progression. Patients need these check-ups for the rest of their lives.

Hospital eye services are very busy, accounting for 10% of all NHS outpatient visits. Glaucoma patients represent a significant part of this workload, in England alone over 1 million visits per year are for glaucoma patients. Providing regular surveillance and treatment is already a major challenge for the NHS. The prevalence of glaucoma increases with age. Demand for glaucoma care is increasing (and will continue to do so) due to our aging population.

Recent advances in technology mean it is now possible for glaucoma patients to monitor eye pressure and visual fields in their own home. Their information could be transferred to the hospital for interpretation by a health care professional, or they could request hospital appointment if the home tests show their glaucoma has worsened or eye pressure has increased. Home monitoring could mean patients requiring fewer hospital check-ups, whilst increasing convenience and potentially reducing costs and increase capacity for the NHS.

Currently though, we do not know if home monitoring is acceptable to people with glaucoma, or if home monitoring in the general glaucoma population is feasible. The main aim of our study is to assess acceptability and feasibility of home monitoring, and to make recommendations about future research to test how the NHS could use home monitoring.

The project detailed in this protocol outlines the first work package (WP1) of a multiphase project. Work package 1 aims to identify which patients would be most appropriate for home monitoring. Frequency of monitoring for glaucoma patients is determined by severity of disease and rate of progression. At the moment it is uncertain which population would benefit most from home monitoring, e.g. those with stable and well controlled disease or those with severe glaucoma at high risk of progression. This first WP will then inform the subsequent phases of the project, which will involve NHS patients and is being reviewed by an NHS REC.

This research fits one of the top five research recommendations by the James Lind Alliance, i.e., "What can be done to improve early diagnosis of sight-threatening glaucoma"? We have included a patient as independent member of the Study Steering Committee who will be actively involved in the conduct and governance of the research. We will also involve the International Glaucoma Society in an advisory role. Results of the study will be shared with those who participated and with relevant stakeholders in Hospital Eye Services.

1.	Introduction
1.1.	Background
	Resource constraints resulting in delays in patients' access to glaucoma services have resulted in vision loss due to glaucoma [1]. Glaucoma services are overwhelmed and struggling to accommodate current demands [8]. Reducing the need for hospital based services will improve the ability to see those most at risk of vision loss, which could alleviate both demand on the service and improve patient outcomes. Digital technologies that provide opportunities for home monitoring of glaucoma progression have potential to contribute to solve these challenges and, potentially, improve outcomes. However, understanding which patients could benefit most, the acceptability of the technologies, and the implications for the service need to be resolved before a definitive evaluative study can be conducted. The feasibility study outlined in this application will address these uncertainties.
	There are recent advances for home monitoring of chronic diseases such as type 1 diabetes (e.g., real-time continuous glucose monitoring, where glucose levels can be accessed electronically by physicians) and high blood pressure (ambulatory blood pressure monitoring, ABPM).
	Glaucoma is the second leading cause of blindness in the UK and it is potentially preventable. Glaucoma is an age-related chronic and progressive eye condition that requires regular monitoring at hospital eye services (HES). When diagnosis of glaucoma is confirmed, treatment with anti-glaucoma therapy is started. Treatment is escalated when there is a diagnosis of progression of disease, typically with visual field testing, or when the intraocular pressure (IOP) is above the individualised target level. When patients receive additional treatment (e.g., additional eye drops) patients are reassessed at each subsequent visit to determine disease stability and IOP control, to decide whether further treatment escalation is necessary.
	Hospital eye services (HES) account for 10% of the NHS outpatient activity, and about ¼ of all outpatient visits to HES are due to glaucoma. Thus monitoring of patients with glaucoma generates a considerable burden for the NHS and for patients. Over £500m is currently spent on glaucoma care in the NHS [9]. This is likely to increase as the population ages and more people develop glaucoma during their lifetime and require longer periods of monitoring as they live longer [8]. Already there is evidence that burden of glaucoma follow-up on the NHS is exceeding resources to undertake it and there is UK-wide data that lack of timely monitoring has resulted in some glaucoma patients losing vision and even progressing to blindness [1]. Evaluations of digital technologies (such as apps) for home monitoring to reduce demand on the service whilst simultaneously improving patient outcomes through earlier detection of disease progression are an urgent priority.
1.2.	Rationale for Study

2.1.	Objectives Primary Objective
2.	Study Objectives
	The project detailed in this protocol outlines the first work package (WP1) of a multiphase project. Work package 1 aims to identify which patients would be most appropriate for home monitoring. Frequency of monitoring for glaucoma patients is determined by severity of disease and rate of progression. At the moment it is uncertain which population would benefit most from home monitoring, e.g. those with stable and well controlled disease or those with severe glaucoma at high risk of progression. In order to identify which patents may be most appropriate for home monitoring we will use vignettes describing different clinical scenarios covering patients with low and high risk of disease progression. Clinical vignettes are simple, efficient tools used to measure variation in clinicians' beliefs, attitudes and behaviours in relation to diagnosis and management of patients with similar conditions . This first WP will then inform the subsequent phases of the project, which will involve NHS patients and is being reviewed by an NHS REC.
	In a new model of care implementing digital technologies in this setting, glaucoma patients would be monitored using the home monitoring tests rather than attending HES. If the tests confirmed that glaucoma is under control further HES visits would not be needed. If the home monitoring tests indicated a deterioration, the patient or the clinician would arrange an appointment and/or a prescription for additional treatment would be issued. Under this new model, the focus of NHS hospital glaucoma clinics would then shift to providing appointments to people with progressing or uncontrolled disease, rather than regular monitoring appointments. However, before the benefits of digital technologies for glaucoma home monitoring are realised the feasibility of their use in practice and the potential benefits for patients and the health care service needs to be assessed.
	Digital technologies are now available for regular monitoring of glaucoma by patients at home. Specifically, applications for self-monitoring of visual function (visual field test) and the Icare HOME technology, which has been developed to measure IOP at home. These technologies are safe, FDA approved and CE marked, and allow data to be acquired at home and potentially transmittable to a hospital without the need for patients to interpret tests results, making home monitoring of glaucoma practicable.
	The need for this research is multipronged and addresses calls from national funders, the Department of Health, and the James Lind Alliance. The work described in our proposal will generate evidence on the feasibility of home monitoring for glaucoma and whether the use of digital technologies in this context have the potential to improve efficiencies for the NHS and self- management for patients.

	Identify which glaucoma patients are most appropriate for home monitoring
	(e.g. all patients, or those with stable disease, or those with severe
	glaucoma?);
2.	Secondary Objectives
2.2.	Outcomes
2.	Primary Outcome
2.	Secondary Outcomes
3.	Study Design
3.1.	Study Description
	An online survey to identify glaucoma patients most suitable for home monitoring will be hosted and disseminated through the Survey Monkey platform. Consultants Ophthalmologists who are members of the Royal College or the UK & Eire Glaucoma Society (UKEGS) will be sent an invitation to participate in the study with a weblink to the survey through the Royal College Ophthalmologists (RCOphth) and the UKEGS distribution lists. The survey will ask clinicians to consider a variety of scenarios or vignettes. In this case the vignettes will take the form of brief narratives containing key items of information about glaucoma severity (mild, moderate, severe), current treatment, disease control (apparently well controlled, uncertain) and management options that are available to fictional patients. These vignettes will be developed by the Research Fellow through discussion with the three clinical leads for each of the recruiting sites in subsequent phases of the project.
	The order of the presentation of the vignettes will be randomised and presented. For each clinical vignette, Consultant Ophthalmologists will be asked to consider whether these patients would be appropriate for home monitoring using the digital technologies being assessed in this application. The data from the clinical vignette will be presented and the consultants will be asked to score a patient as either 'Appropriate'/'Not appropriate'/'Unclear' for home monitoring. If 'unclear' is selected further information will be requested (through open text comments boxes) for justification of this response.
3.2.	Study Flowchart
	Study Matrix
3.3.	

4.	Study Population
4.1.	Number of Participants
	The survey will be hosted and disseminated through the online Survey Monkey platform . Consultants Ophthalmologists who are members of the Royal College or the UKEGS will be sent an invitation to participate in the study with a weblink to the survey through the Royal College Ophthalmologists (RCOphth) and UKEGS distribution lists. The RCOphth and UKEGS distribution lists have previously been utilised for disseminating surveys for research purposes and the RCOphth have agreed to disseminate our survey. The RCOphth list can facilitate dissemination to approximately 100 clinical lead Consultant Ophthalmologists with a predicted response rate based on other RCOphth administered surveys of 45%. The UKEGS will enrich the sample for Consultant Ophthalmologists who are currently specialising in treating patients with glaucoma. We aim to recruit a suitable number of Consultant Ophthalmologists who are representative of those working in the UK and making decisions about the clinical care of patients with glaucoma.
4.2.	Inclusion Criteria
	Consultant Ophthalmologists who currently treat patients with glaucoma and are members of and included on the distribution list for the Royal College of Ophthalmologists.
4.3.	Exclusion Criteria
5.	Participant Selection and Enrolment
5.1.	Identifying Participants
	Consultants Ophthalmologists who are members of the Royal College or UKEGS will be sent an invitation to participate in the study with a weblink to the survey through the Royal College Ophthalmologists (RCOphth) and UKEGS distribution lists. The RCOphth and UKEGS distribution list has previously been
	utilised for disseminating surveys for research purposes
5.2.	utilised for disseminating surveys for research purposes Consenting Participants
5.2.	
	Consenting Participants
5.3.	Consenting Participants Screening for Eligibility
5.3. 5.4.	Consenting Participants Screening for Eligibility Ineligible and Non-Recruited Participants
5.3. 5.4. 6.	Consenting Participants Screening for Eligibility Ineligible and Non-Recruited Participants Randomisation and Blinding

6.3.	Withdrawal Procedures
	The only withdrawal criteria for the study would be that a participant does not regularly treat patients with glaucoma.
	If a participant is required to be withdrawn from the study (either through study exclusion or withdrawal of consent), aggregate level data on reason for exclusion will be collected, no direct efforts to replace individuals will be made, and data will be retained with the appropriate permissions as detailed in the PIL.
7.	Study and Safety Assessments
	This phase of the research is a staff only survey about identification of appropriate glaucoma patients who would be eligible for home monitoring. It does not raise any substantial safety issues.
8.	Data Collection and Management
8.1.	Data Collection
	Data will be collected through the online Survey monkey platform. Data downloads from the platform will be stored securely on a password protected shared drive on a University of Aberdeen server.
8.2.	Data Management System
	Participants will be assigned a unique identifier on their questionnaire. All electronic resources will be stored on the University of Aberdeen server, with access restricted to the study team.
9.	Labs and Samples Analysis
9.1.	
10.	Statistics and Data Analysis
10.1.	Sample Size Calculation
	No formal sample size has been calculated as the purpose of this survey is expert opinion. The sample will be a convenience sample generated from the membership of the Royal College of Ophthalmologists.
10.2.	Proposed Analysis
	Data will be analysed using descriptive statistics and reported using frequencies to identify which cases there is most agreement as being appropriate for home monitoring. Vignettes for which there is more than 50% of respondents listing as 'Unclear', analysis of the free text will be conducted using a content analysis approach to determine whether and how the patients presented in these vignettes could be suitable for home monitoring.
10.3.	Missing Data

10.4.	Transfer of Data
11	Trial (Study Managament and Oversight Arrangements
11.	Trial/Study Management and Oversight Arrangements
11.1.	Trial/Study Management Group
	The overall multi-stage study will be co-ordinated by a Study Management Group, consisting of the grant holder (CI), coapplicants, external PIs, PPI partner, and Research Fellow.
11.2.	Trial/Study Management
	A Research Fellow will oversee the study and will be accountable to the CI. The Research Fellow will be responsible for checking the completeness, plausibility and consistency of the data. However, this remains the overall responsibility of the CI. Any queries will be resolved by the CI or delegated member of the study team.
11.3.	Trial/Study Steering Committee
	An independent Study Steering Committee (SSC) will be established to oversee the conduct and progress of the entire study as per the recommendations from the funder.
11.4.	Data Monitoring Committee
	An independent Data Monitoring Committee (DMC) is not required for this study as confirmed by the funder.
12.	Inspection of Records
12.1	The CI, PIs and all institutions involved in the study shall permit study related monitoring, audits, and REC review. The CI agrees to allow the Sponsor or, representatives of the Sponsor, direct access to all study records and source documentation.
13.	Good Research Practice
13.1.	Ethical Conduct of the Study

	The study will be conducted in accordance with the principles of good clinical practice (GCP). In addition to Sponsorship approval, a favorable ethical opinion has been obtained from the appropriate REC prior to commencement of the study. CERB/2020/5/1963
13	Confidentiality
	All records will be identified in a manner designed to maintain participant confidentiality. All records will be kept in a secure storage area with limited access to study staff only.
	The CI and study staff involved with this study will not disclose or use for any purpose other than performance of the study, any data, record, or other unpublished, confidential information disclosed to those individuals for the purpose of the study. Prior written agreement from the Sponsor or its designee will be obtained for the disclosure of any said confidential information to other parties.
13	Data Protection
	The study team involved with this project will comply with the requirements of the General Data Protection Regulations (GDPR) and the Data Protection Act 2018. The HRA recommended wording to fulfil transparency requirements under the GDPR for health and care research will been included in the survey.
	The CI and study staff will also adhere, if appropriate, to the current version of the NHS Scotland Code of Practice on Protecting Patient Confidentiality. Access to collated participant data will be restricted to the CI and appropriate study staff.
	Computers used to collate the data will have limited access measures via user names and passwords.
	Published results will not contain any personal data that could allow identification of individual participants.
13	Insurance and Indemnity

	The University of Aberdeen is sponsoring the study.
	Insurance
	• The University of Aberdeen will obtain and hold a policy of Public Liability Insurance for legal liabilities arising from the study.
	Indemnity: The Sponsor does not provide study participants with indemnity in relation to participation in the Study but has insurance for legal liability as described above.
14.	Study Conduct Responsibilities
14.1.	Protocol Amendments, Deviations and Breaches
	The CI will seek approval for any amendments to the Protocol or other study documents from the Sponsor (in the first instance), REC and NHS R&D Office(s). Amendments to the protocol or other study documents will not be implemented without these approvals.
	In the event that a CI needs to deviate from the protocol, the nature of and reasons for the deviation will be recorded in the CRF, documented and submitted to the Sponsor. If this necessitates a subsequent protocol amendment, this will be submitted to the Sponsor for approval and then to the appropriate REC and lead NHS R&D Office for review and approval.
	In the event that a serious breach of GCP is suspected, this will be reported to the Sponsor immediately using the form "Breach Report Form".
14.2.	Study Record Retention
	Study documents will be retained for 5 years after study end date.
14.3.	End of Study
	The end of study is defined as completion of data analysis and study reporting. The Sponsor, CI and/or the TSC have the right at any time to terminate the study for clinical or administrative reasons.
	The end of the study will be reported to the Sponsor and REC within 90 days, or 15 days if the study is terminated prematurely. The CI will ensure that any appropriate follow up is arranged for all participants.
	A summary report of the study will be provided to the Sponsor and REC within 1 year of the end of the study.
15.	Reporting, Publication and Notification of Results
15.1.	Authorship Policy

	Ownership of the data arising from this study resides with the study team and their respective employers. On completion of the study, the study data will be analyzed and tabulated, and a clinical study report will be prepared.
15.2.	Publication

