	RO1 - Understand the views of patients and clinicians on whether digital technologies for glaucoma home monitoring would be feasible and acceptable. Patients Patients Patients with glaucoma who are being treated at one of the three NHS sites (NHS Lothian, Nottingham University Hospital Trust, Belfast Health and Social Care Trust). Clinical parameters to specify which patients to consider for inclusion (e.g. those with slow progression of disease)will be identified during a linked but separate survey of Consultant Ophthalmologists (received
	favourable opinion by University of Aberdeen's CERB committee - CERB/2020/5/1963). Ophthalmologists Consultant Ophthalmologists currently responsible for regular monitoring of glaucoma patients.
	Researchers and NHS Staff Research teams who have or are evaluating digital technologies for home monitoring of eye disease e.g. macular degeneration (e.g., MONARCH, HTA 15/97/02). Research Nurses involved in our feasibility study tasked with delivering the home monitoring training will also be invited to interview along with IT personnel from the relevant Trusts.
	RO2 – Developing a conceptual framework for the economic evaluation of home monitoring glaucoma. Healthcare staff Staff directly involved in HES monitoring e.g. clinicians, nurses, and administrative staff.
	Patients As above for RO1 – same patients.
19.3.	Exclusion Criteria
	Participants who are unable to give informed consent to participate and participants who are unable to understand English.
	There are no specific exclusion criteria
20.	Participant Selection and Enrolment
20.1.	Identifying Participants

	RO1 - Understand the views of patients and clinicians on whether digital technologies for glaucoma home monitoring would be feasible and acceptable. Patients Patients Patients will be identified through clinical case load lists from the three recruiting centres: Edinburgh, Nottingham, and Belfast. Research Nurses at each site will identify potentially eligible participants.
	Ophthalmologists Ophthalmologists who have previously expressed an interest in participating the research and consented to further contact via a linked survey (received favourable opinion by University of Aberdeen's CERB committee - CERB/2020/5/1963) will be approached to participate in the focus groups.

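### WP1 plans content analysis of the 'Unclear' comments only where 'Unclear' passes 50%, a cut-off narrower than its stated purpose when there are three response options

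*Protocol*

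**What the plan says.** WP1 section 3.1 (Study Description) has each consultant "score a patient as either 'Appropriate'/'Not appropriate'/'Unclear' for home monitoring". Only one answer brings a request for reasons: "If 'unclear' is selected further information will be requested (through open text comments boxes) for justification of this response".

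WP1 section 10.2 (Proposed Analysis) then sets out two steps. The first covers all vignettes: "Data will be analysed using descriptive statistics and reported using frequencies to identify which cases there is most agreement" on being appropriate for home monitoring. The second is conditional: the free text is analysed for vignettes with "more than 50% of respondents listing as" 'Unclear'. It uses a content analysis approach, and its aim is "to determine whether and how the patients presented in these vignettes could be suitable for home monitoring". The section names no other use of the free text.

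The result is carried forward. In the WP2-4 protocol, section 19.2 (Inclusion Criteria) says of patients: "Clinical parameters to specify which patients to consider for inclusion" will be identified in the linked consultant survey, which is WP1. The section on screening for eligibility has research nurses apply those parameters.

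**The concern.** A simple-majority trigger is natural when there are two possible answers. Here there are three, and 'Unclear' can lead the count with little more than a third of the replies. A vignette can also split so that no answer passes one half. In neither case need the trigger be met, and in the second it cannot be.

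The stated purpose of the content analysis is to learn whether and how the patients described could be suitable. That question is as open for a vignette scored 35% 'Appropriate', 25% 'Not appropriate' and 40% 'Unclear' as for one scored 0%, 49% and 51%. Only the second would be examined, although the first has more support for home monitoring.

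WP1 has one objective, to identify which patients are most appropriate, and its output informs the WP2-4 clinical parameters. For a vignette without a clear answer, a bare frequency gives the least guidance, and the reasons already requested from the uncertain respondents would help most. The cut-off is written into the protocol, so this is not a detail left to a later analysis plan.

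**Working it through.** **Inputs from the protocol**
- Response options per vignette: 3 (WP1 section 3.1).
- Free text requested from: 'Unclear' respondents only (WP1 section 3.1).
- Trigger: 'Unclear' above 50% of respondents (WP1 section 10.2).
- Replies: the Royal College list reaches about 100 clinical leads with a predicted response of 45% (WP1 section 4.1), so 100 × 0.45 = 45. UKEGS members are added without a number, so 45 is not a predicted total.
- WP1 has no formal sample size (section 10.1), so there is no power figure to reproduce.

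**Inputs that are assumptions:** the true shares choosing each answer. The protocol gives none.

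**Step 1: the logic, which needs no assumption.** If no option exceeds 50%, then 'Unclear' does not exceed 50% and the rule cannot fire. Enumerating all splits of n replies over three answers confirms this:

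| n | All splits | Splits with no majority | Of these, rule fires |
|---|---|---|---|
| 45 | 1,081 | 253 | 0 |
| 60 | 1,891 | 496 | 0 |
| 100 | 5,151 | 1,326 | 0 |

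At n = 45, 'Unclear' is strictly the commonest answer in 77 of the 253 no-majority splits. One example is 16 'Appropriate', 11 'Not appropriate' and 18 'Unclear' (36%, 24%, 40%).

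**Step 2: what stays outside the plan.** At n = 45 the rule needs at least 23 'Unclear' replies (23/45 = 51.1%; 22/45 = 48.9% is not enough). Up to 22 requested justifications on one vignette can therefore have no planned analysis. Each no-majority split at n = 45 has between 1 and 22 'Unclear' replies.

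**Step 3: how often the rule fires, on assumed shares.** With X ~ Binomial(45, p) and p the true 'Unclear' share, P(fires) = P(X ≥ 23):

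| p | P(fires) |
|---|---|
| 1/3 | 0.010 |
| 0.40 | 0.086 |
| 0.45 | 0.249 |
| 0.50 | 0.500 |
| 0.55 | 0.751 |

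**Step 4: how often there is no majority, on assumed shares.** With true shares of 35/25/40 ('Appropriate'/'Not appropriate'/'Unclear'), summing the exact multinomial probabilities over all splits with no count above 22 gives 0.894 at n = 45.

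**Step 5: more replies do not cure it.** With the same 35/25/40 shares and n taken as an assumption:

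| n | Count needed to fire | P(fires) | P(no majority) |
|---|---|---|---|
| 45 | 23 | 0.086 | 0.894 |
| 60 | 31 | 0.045 | 0.950 |
| 100 | 51 | 0.017 | 0.983 |

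**The case against.** **Section 10.2 ranks; it does not label.** It reports frequencies to see where agreement on 'Appropriate' is highest. No vignette is declared settled at 50%, so a missing majority is not in itself a gap. This stands. The point rests on the mismatch between the content analysis and its own stated aim, not on a missing consensus rule.

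**The comments cannot explain a split between the definite answers.** A reader might infer that the plan gives up the reasons behind disagreement over 'Appropriate' and 'Not appropriate'. The protocol does not support that: those respondents are never asked why. The comments bear only on the uncertain share.

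**Nothing is said to be discarded.** A reader might also infer that the remaining comments will go unread. Section 10.2 says when a content analysis will be done; it does not forbid reading or summarising the rest, and all vignettes are reported as frequencies. What can be said is that no analysis of the other comments is planned.

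**The percentages are illustrative.** A rule set above 50% seldom fires when the true share is below 50%, by design. The shares are hypothetical, and 45 covers one of two distribution lists. This stands for steps 3 to 5 but leaves steps 1 and 2 untouched.

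**Harm to eligibility is not shown.** WP1 is a descriptive convenience survey that informs a purposive feasibility sample. The protocol states no mechanical route from a vignette's majority to inclusion, so it would be too strong to say that patient types will be wrongly included or excluded.

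**A different majority cut-off has its own gaps.** A trigger of neither definite answer exceeding 50% would fire on 22/22/1, where there is at most one comment to read, and would miss 23/0/22, where up to 22 were requested. This stands, and it is why removing the cut-off is better than moving it.

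**Conclusion.** The point holds as a minor one. By simple logic, the section 10.2 trigger cannot fire for a vignette without a majority, and it can fail to fire when 'Unclear' is the commonest answer. In those cases the justifications have no planned analysis, while the question they were meant to inform remains open.

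The size can only be illustrated: with 45 replies, the rule fires 9% of the time at a true 'Unclear' share of 40% and 25% of the time at 45%. Those figures rest on assumed shares and on the Royal College list alone. What is lost is a planned reading of the uncertain respondents' reasons for some vignettes. The frequencies are not lost, and the two definite camps were never going to be explained by this text. It is a cheap improvement to make before the survey is used to set the WP2-4 parameters, not a threat to the study.

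**What to change.** In WP1 section 10.2, remove the 50% condition and apply the content analysis to the 'Unclear' free text of every vignette. State that its results will be used alongside the frequencies when the WP2-4 clinical parameters are set.

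If a trigger is wanted to limit the work, the minimum is any vignette where 'Unclear' is the commonest answer or where neither 'Appropriate' nor 'Not appropriate' exceeds 50%. This contains every vignette the present rule selects, since 'Unclear' above 50% forces the other two below it. It would still leave out a vignette such as 23/0/22, so analysing all the 'Unclear' text is preferable.

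Neither version needs new data or a change to the survey. The cost is some extra coding of short comments. At 45 replies, that is at most 22 for each vignette the present rule would leave out; with UKEGS replies the ceiling rises to half of the total replies.
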